Lost to Contact

If a participant is lost to contact for 2 weeks, the research coordinator will try to contact them via all modes of communication, including personal phone, emergency contact, text, email, and postal service.

If the participant is lost for an additional 2 weeks (a total of 4 weeks), then they will be considered lost and dropped from the study.

If a participant is randomized to a treatment group but makes no contact in the first week, they will be dropped from the study.

If a participant withdraws or is dropped from the study, the research coordinator documents the date and reason in the Portal. This information will be summarized annually for the site-specific IRBs as well as for the Shepherd (Primary site) IRB, the Advisory Board, and the Data Safety Monitoring Board (DSMB), and will be reported in the Final Project report. We will not automatically replace withdrawals, but will develop a strategy based on the attrition rate after the first few waves have completed the study.

Other Withdrawals

To assist with the study intent to treat analyses, the study will attempt to collect data from withdrawals. Research Coordinators will offer participants who withdraw three options:

- 1) Early Termination Visit: Participants will return to the facility to complete a full set of CRO and PRO assessments (including the feedback survey) and subsequently their withdrawal will be processed. Participants receive the \$25 travel stipend for the visit.
- 2) Continue with assessments only: Participants will cease the exercise program but continue with assessments on schedule and per protocol.
- 3) Complete an immediate withdrawal: Participants withdraw immediately and fully from both the exercise program and assessments.

Should a participant choose 1) or 2), they will sign a new consent form with information about participating in these withdrawal assessments (ICF Withdrawal – Early Termination Visit or ICF Withdrawal – Assessments Only).

INTERVENTION

There are two modes of delivering the evidence-based, individualized exercise program: Facility-based exercise training (GEMS-S) and Telerehab-based exercise training (GEMS-T). GEMS-S will be delivered at each of the eight recruiting sites (n=200) and GEMS-T will be delivered via UAB within a participant's home/community (n=200). Both GEMS-S and GEMS-T consist of an identical, individualized exercise program based on evidence-based exercise guidelines.

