Participants will undertake both aerobic and resistance training of moderate intensity twice per week for 16 weeks (4 months), based on these conditions:

- a. The prescription is individualized, based on each participant's ability. All participants are provided a low-level prescription to try for one week. They are asked to monitor how they feel, and at the end of the first week, they are contacted by a coach (GEMS-S participants in person at the facility; GEMS-T participants via video-chat). The goal is for the participant to gradually progress toward meeting the exercise guidelines.
- b. The elements of the intervention were chosen to facilitate self-management of exercise, as well as to maintain the integrity of the intervention across delivery modes (GEMS-S and GEMS-T). All participants will receive a hip-worn pedometer to monitor steps. This information is to monitor fidelity of the exercise implementation only, and the participant will also record this information on their adherence log for each session. For aerobic training, the walking speed in the natural environment (GEMS-T) are adjusted to get the desired 100 steps/minute and target heart rate (HR) based on HR reserve and target zones

defined by the American College of Sports Medicine.⁴⁴ The target stepping rate and HR correspond to moderate-intensity exercise in persons with MS.

- c. Resistance training consists of 1-2 sets, 10-15 repetitions of 10 exercises targeting lower body, upper body, and core muscle groups performed 2 days per week. Participants start with the amount of resistance at which they can perform 10-15 repetitions. GEMS-T participants will receive bands to use at home, and GEMS-S participants will be given bands to use and keep by each site.
- d. There are three separate levels of difficulty of the exercise intervention (orange, blue, white) that the participant chooses in discussion with their behavioral coach. This mutual decision is based on participants' experience following the first two weeks of the program and coaches' perception of how they did. The levels of difficulty vary in terms of progression toward meeting the exercise guidelines. This feature is critical for accommodating the various levels of ability we anticipate for our participants. Much like those who do not have a disability, each participant may start at a different level; the goal is for each participant to exercise at moderate intensity by week 10 of the intervention.

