If a physician instructs a participant to pause exercising, the site research coordinator must obtain medical clearance from the participant's physician before resuming exercise. If the participant's physician does not instruct a participant to stop exercising, the site PI determines whether or not medical clearance after an AE is required.

Site research coordinators will inform the participant's coaches when medical consent has been obtained and the participant is approved to resume exercising.

Figure 3 below provides additional detail regarding how AEs are reported and addressed.

[figure not shown]
[figure not shown]

Figure 3: AE Reporting and Follow up Procedures

DATA ANALYSIS

Data analysis plan

The primary hypothesis is a non-inferiority test of the changes in T25FWT between GEMS-T and GEMS-S. This will be tested using a linear model with site as the stratification factor and an intention to treat approach. The primary analysis will adjust for covariates age, gender and baseline EDSS or PDDS. Further addition of covariates may be examined in sensitivity analyses based on any differences seen on examination of baseline variables between groups. Secondary endpoints include change in 6MWT and EDSS/PDDS. In all endpoints, we are assessing

improvement over baseline values. We will examine the frequency of worsening as a safety comparison. We will also examine the primary endpoint of a 20% improvement in the T25FWT (yes or no) using logistic regression. Further, to characterize the changes over time, we will use linear mixed models to assess the slopes of change for GEMS-S versus GEMS-T groups. We will also examine the relationship between the dose of exercise measured by compliance and the change in the primary and secondary outcomes. These are exploratory outcomes to see if the compliance measures predict the benefits on the outcomes. This information is important for translation and information dissemination to people with MS.

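### Randomised participants who fall silent are dropped from outcome follow-up as well as from the programme, so those lost before week 16 have no follow-up walk test in an intention-to-treat analysis; the size and direction of any bias are unknown

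*Protocol*

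**What the plan says.** The protocol section on withdrawals and dropped participants has two parts.

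- **Lost to Contact, search step.** "If a participant is lost to contact for 2 weeks, the research coordinator will try to contact them via all modes of communication". After two further weeks of silence, "they will be considered lost and dropped from the study".
- **Lost to Contact, first-week rule.** "If a participant is randomized to a treatment group but makes no contact in the first week, they will be dropped from the study". No search is attached to this rule, and it does not say whether the week runs from randomisation or from the start of exercise.
- **Other Withdrawals.** "To assist with the study intent to treat analyses, the study will attempt to collect data from withdrawals". Three options follow, addressed to those who withdraw: an early termination visit, assessments without the exercise programme, or complete withdrawal. The first two need a new signed consent form.

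Under Enrollment, randomisation is the last step of enrolment and follows the baseline measures. Under Intervention, item a, all participants start with a low-level prescription and "at the end of the first week, they are contacted by a coach", in person for GEMS-S and by video-chat for GEMS-T. Table 1 schedules the T25FWT at Visit 1, 16 weeks and 12 months.

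On the primary non-inferiority comparison, the protocol's Data analysis plan says: "This will be tested using a linear model with site as the stratification factor and an intention to treat approach". The SAP makes the same commitment.

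**The concern.** Both silence rules end participation in the study, not only in the exercise programme. The protocol knows the difference, because its assessments-only option is built on it and is justified by the intention-to-treat analysis. Yet that option is addressed to people who announce that they are leaving. Those who simply go quiet are not mentioned.

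The result is a post-randomisation exclusion that depends on engagement. People who do not engage with an exercise programme may well have different walking outcomes from those who do. A non-inferiority comparison that is called intention to treat, but lacks observed outcomes for such a group, rests on an untested assumption about them. SA2 is exposed too: it asks how choice affects outcomes, adherence and dropout, and silence after allocation could be related to whether a participant got the preferred mode.

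**Working it through.** There is no figure in the plan to reproduce. The 400 participants are stated without a margin, standard deviation, alpha, power or expected dropout. The check is therefore mainly textual, with arithmetic for timing and for assumed scenarios.

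**1. Order of events.** The first-week drop falls at week 1 and the all-modes search starts at week 2, so a first-week non-contact is closed before the search would begin. If the week is counted from the start of exercise, the drop also falls at about the time of the first scheduled coach contact.

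**2. What is still ahead.** Counting from the start of exercise, the walk tests fall at week 16 and, 12 months after the intervention, at week 16 + 52 = 68.

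| Drop | Weeks to 16-week test | Weeks to 12-month test |
|---|---|---|
| First-week rule | 16 − 1 = 15 | 68 − 1 = 67 |
| Four-week rule, silent from the start | 16 − 4 = 12 | 68 − 4 = 64 |

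A drop before week 16 leaves no T25FWT after randomisation. A drop after week 16 leaves the 16-week result in place and loses only the 12-month walk test.

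**3. What the SAP does with such a participant.** Two rules apply and they disagree.

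- *Sensitivity analyses:* the model-based timed-walk endpoint is imputed only for people who have a walk test after randomisation. An early drop has none and is outside this rule.
- *Management of missing data, item b:* below 3% missing, complete cases are used; above 3%, multiple imputation is used throughout. Counted in participants, 3% is 0.03 × 400 = 12, so with fewer than 12 missing they are left out. Above that they are imputed assuming missing at random, largely from participants who stayed engaged.

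The SAP does not say which rule governs a participant with baseline data only.

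**4. Bias, formula only.** Let d be the share dropped in a mode, and g the mean improvement of retained minus dropped participants. The mean over everyone is (1 − d) × retained mean + d × dropped mean = retained mean − d × g. The observed-only mean is therefore too favourable by d × g, and the mode difference is off by

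error = dT × gT − dS × gS (positive favours GEMS-T).

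All rates and gaps below are assumed:

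| dT | dS | g, both modes (SD) | Error (SD) |
|---|---|---|---|
| 5% | 5% | 0.5 | 0 |
| 10% | 5% | 0.5 | 0.050 − 0.025 = +0.025 |
| 5% | 10% | 0.5 | 0.025 − 0.050 = −0.025 |
| 15% | 5% | 1.0 | 0.15 − 0.05 = +0.10 |

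The sign follows whichever mode loses more, and unequal gaps would produce an error even at equal rates.

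**5. Precision, also assumed.** With one-sided alpha 0.025 and a true difference of zero, power after losing a share d is Φ((z₀.₉₇₅ + z_power) × √(1 − d) − z₀.₉₇₅). At d = 10%, 360 of 400 remain; a design with 80% power falls to 75.7% and one with 90% to 86.8%. At d = 5%, 380 remain and the figures are 78.0% and 88.5%.

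**The case against.** The best defence has four parts.

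- **Silence is chased in both modes.** The site coordinator notifies everyone of the assignment, coaches in both modes make contact at the end of week 1, GEMS-S coaches call after a missed session, and the GEMS-T coordinator follows up missing logs. The four-week rule is preceded by a search through every channel. This stands, and it should keep numbers down. It does not add a search before the first-week drop or an assessment after either drop.
- **The SAP plans for missing data.** It has multiple imputation with a missingness propensity score, per-protocol, best-case and worst-case analyses, and two methods that depart from missing at random. These help interpretation and mean that dropped participants need not vanish from the analysis. They do not recover outcomes that were never sought.
- **The heading Other Withdrawals may imply that lost contact is itself a withdrawal**, and nothing forbids offering the options to someone who resurfaces. That is a fair reading, but it is nowhere stated, and two sites could act differently.
- **The first-week clock is undefined.** The protocol allows up to 60 days from Visit 1 to starting exercise, so the coincidence with the first coach contact is one reading only.

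A reader might go further and infer that the rule falls mainly on GEMS-T and so biases the test towards non-inferiority. The documents do not support that. Both modes have contact attempts, and the Background says that poor access can make facility programmes hard to engage in, so GEMS-S could lose more and the error would reverse. A reader might also infer that ignoring the 6-month surveys leads to a drop before the 12-month walk. The four-week rule has no end date, but the protocol does not equate unanswered surveys with lost contact, and it sends reminders up to a deadline.

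**Conclusion.** The point holds as a gap in outcome collection. Read as written, the protocol stops seeking outcomes from an engagement-selected subset of randomised participants, while the primary analysis is called intention to treat and the SAP gives two incompatible treatments for those without a walk test after randomisation. This does not depend on any assumed rate.

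Its size does. The documents give no drop rates and no outcome gap, so neither the magnitude nor the direction of bias can be stated. Among the assumed scenarios the error runs from zero to 0.10 SD, and the same formula can favour either mode. At low drop rates it would be small. The case for acting is that the repair is cheap and that an assessment not attempted cannot be recovered later by analysis.

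**What to change.** In the protocol, under Lost to Contact:

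1. Separate stopping the programme from stopping outcome follow-up. When coaching ends is for the sponsor to decide and need not change.
2. Apply the all-modes search to first-week non-contacts before any closure, and define when the first week starts.
3. Attempt the scheduled 16-week, 6-month and 12-month assessments for every randomised participant unless consent to assessments is withdrawn, using the existing reminders and visits. Cover this in the main consent form or through the existing assessments-only consent.

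In the SAP:

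4. Define the intention-to-treat set as everyone randomised, analysed in the assigned mode, or the chosen mode for the Choice group.
5. Reconcile the timed-walk rule under Sensitivity analyses with the general rule under Management of missing data, stating what is done for participants with baseline data only.

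The cost is consent-form wording, which may need ethics review, and a few more coordinator contacts per silent participant. Reported missing-visit counts will also look higher, because silent participants stay in the denominator.

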- GEMS-T participants will continue with their virtual coaching and exercise sessions on schedule. GEMS-T coaches will add advice to their coaching sessions relating to how to exercise while maintain safe COVID-19 social distancing measures. They will also log any interruptions in training related to COVID-19.
- Any participants enrolled in wave 9 will not begin exercising until site COVID-19 restrictions are lifted. Research coordinators will call wave 9 participants and let them know that they will contact them again when the study resumes exercising. Depending on when this is, participants may require further screening.

Behavioral Training

The physical exercise program is supplemented with a behavioral training intervention developed by Motl et al., based on Social Cognitive Theory (SCT) in people with MS.⁵⁶ The behavioral component entails regular meetings with MS exercise specialists (i.e., behavioral coaches), informational newsletters, detailed training manuals, and log books for self-monitoring. Personal interactions with coaches are conducted in person for GEMS-S participants and via one-on-one, semi-structured, online video-chat sessions for GEMS-T participants using web cameras and a HIPAA compliant teleconference system based on participant resources and preferences. If participants do not have access to the internet, the video-chats are replaced with phone calls. The in-person and online video-chat sessions will coincide with delivery of newsletters and supplement the content of the newsletters. The newsletters provide instructional material, websites for more information, testimonials of individuals who have experienced benefits of exercise, and tips for participants to try at home. GEMS-S participants will receive newsletters in person and GEMS-T participants will receive them electronically.

The sessions with the coach are designed to provide participants with feedback and information on how to progress through the exercise program as well as social accountability. Coaches will be research staff at each site for GEMS-S and at UAB for GEMS-T. Participants will be assigned to one coach based on availability. Before beginning the study, coaches will receive training from [name] in behavior change for physical activity, and this will be comprised of information regarding SCT and its application for motivating ongoing behavior change through supportive accountability and discussions of newsletter content. We will maximize consistency among coaches by using standardized scripts for guiding each video-chat. The scripts will contain (a) questions to obtain feedback from participants on progress in the program, (b) confirmation of receipt and reading of the relevant newsletter (c) discussion points linked with the relevant newsletter, and (d) opportunities for participants to ask any questions. Coaches will meet weekly and discuss interactions with participants to facilitate cohesion on how coaches respond to participants' needs, questions and experiences.

Coach auditing

Coaching sessions will be audited to ensure that coaches are delivering the intervention as intended. Once per week, on coaching weeks (when coaches discuss newsletters), a coach will randomly choose a coaching session to audio record. A different participant will be audited each time a coaching session occurs. Coaches may record sessions on whichever recording device they choose, as long as it is in compliance with site IRB regulations.

Prior to audio recording, the coach will obtain the participant's permission by asking the participant to sign the HIPAA authorization and release agreement to be audio-recorded.

UAB will review the audio and conduct the audit using a coaching audit checklist. Subsequently, UAB will then provide feedback to the coaches via email.

See Data Safety and Adequacy section below for details on how the audio will be securely shared with UAB and audio recording security measures.

ADVERSE EVENT MANAGEMENT

We define adverse events as follows:

- Adverse Event - Any untoward medical event occurring in a patient or subject enrolled in a clinical trial, regardless of whether the event has a causal relationship with the treatment under investigation.
- Serious Adverse Event - Any adverse experience that results in any of the following outcomes: death, a life-threatening event, requires or prolongs inpatient hospitalization, results in persistent or significant disability/incapacity. Important medical events that may not result in death, be life-threatening or require hospitalization may be considered a serious adverse event when: a) they may jeopardize the patient or subject, b) may require medical or surgical intervention to prevent one of the outcomes listed in this definition, or c) a reasonable possibility exists that the event may have been caused by the test article.

Ongoing reporting of adverse events (AEs) and serious adverse events (SAEs) to the IRB and PCORI will follow the policies and procedures of the Shepherd Center, as outlined in policy AC.RES.01.06 "Unanticipated Problem, Death, and Adverse Event Reporting" and participating IRBs. Specifically:

- The Study PI is responsible for accurate and timely reporting of adverse events in the source documentation. The PI is responsible for reporting SAEs and unanticipated problems (UPs) to the IRB within 10 days of their occurrence.
- Site Co-Investigators are responsible for reporting SAEs and UPs to the study PI at Shepherd within 72 hours using the portal AE form. For SAEs and UPs only, the reporting site personnel should also send an email to the study PI, site PI, coach, research coordinator, and the study Project Manager to ensure all receive timely notification.
- Either coaches or research coordinators can file the AE/SAE form on the portal and must communicate with each other to ensure the report is filed within the required timeline (see Table 3). If coaches start an AE form, they should simultaneously email the site research coordinator with a description of the event and the research coordinator will complete follow up and submit the form.
- All study investigators are responsible for recording all new clinical experiences, exacerbations, and/or deterioration of any existing clinical condition occurring after a study subject has signed informed consent. Research staff will also provide follow-up information on all adverse events until resolution or an appropriate endpoint is reached.
- Adverse Events will be documented and reported as follows:
 - Participant experiences an event, logs a description of the event in their participant diary/log and immediately contacts his/her coach or site research

coordinator, who follows the site-specific reporting steps (see Table 3 and Figure 3).

- The UAB Project Coordinator checks the exercise logs weekly for GEMS-T participants and identifies an AE, and follows the reporting steps in Table 3 and Figure 3. Or,
- Participant experiences an event while with his/her coach, and the coach logs the event and follows the site-specific next steps (Table 3 and Figure 3).

Table 3. Unanticipated Problem, Death, and Adverse Event Reporting (AC.RES.01.06)

Internal Event	Reporting Timeline
Internal Death of any subject	Report promptly within 72 hours of site's knowledge of event using the portal AE form and send email to study PI, site PI, Project Manager (PM), and site research coordinator (RC). PM reports to Shepherd RRC within 10 calendar days using Shepherd Research Review Committee (RRC) "UP, Death & SAE Report Form."
Internal Unanticipated Problem (UP)	Report promptly within 72 hours of site's knowledge of event using the portal AE form and send email to study PI, site PI, PM and RC. PM reports to Shepherd RRC within 10 calendar days using Shepherd RRC "UP, Death & SAE Report Form" on the study Portal.
Internal Serious Adverse Event (SAE) (non-UP)	Report promptly within 72 hours of site's knowledge of event using the portal and send email to study PI, site PI, PM and RC. PM reports to Shepherd RRC within 10 calendar days using Shepherd RRC "UP, Death & SAE Report Form."
Internal Adverse Event (AE) that is Not Serious	
Do not report to RRC. Record event using the AE reporting form on the study Portal within 10 days of initial report.
 
Note: An Adverse Event that is not serious by definition may be reported promptly, if in the opinion of the investigator, the event occurred with greater frequency, duration, or at a higher level of severity than expected.

Internal Unanticipated Adverse Device effect (UADE)	Report promptly within 10 calendar days of site's knowledge of event using Shepherd RRC "UP, Death & SAE Report Form" on the study Portal.
Internal Investigational New Drug Safety Reports, i.e. investigator initiated	If the report meets the criteria for UP, report promptly within 10 calendar days of site's knowledge of event using Shepherd RRC "UP, Death & SAE Report Form" on the study Portal

If a physician instructs a participant to pause exercising, the site research coordinator must obtain medical clearance from the participant's physician before resuming exercise. If the participant's physician does not instruct a participant to stop exercising, the site PI determines whether or not medical clearance after an AE is required.

Site research coordinators will inform the participant's coaches when medical consent has been obtained and the participant is approved to resume exercising.

Figure 3 below provides additional detail regarding how AEs are reported and addressed.

[figure not shown]
[figure not shown]

Figure 3: AE Reporting and Follow up Procedures

DATA ANALYSIS

Data analysis plan

The primary hypothesis is a non-inferiority test of the changes in T25FWT between GEMS-T and GEMS-S. This will be tested using a linear model with site as the stratification factor and an intention to treat approach. The primary analysis will adjust for covariates age, gender and baseline EDSS or PDDS. Further addition of covariates may be examined in sensitivity analyses based on any differences seen on examination of baseline variables between groups. Secondary endpoints include change in 6MWT and EDSS/PDDS. In all endpoints, we are assessing

improvement over baseline values. We will examine the frequency of worsening as a safety comparison. We will also examine the primary endpoint of a 20% improvement in the T25FWT (yes or no) using logistic regression. Further, to characterize the changes over time, we will use linear mixed models to assess the slopes of change for GEMS-S versus GEMS-T groups. We will also examine the relationship between the dose of exercise measured by compliance and the change in the primary and secondary outcomes. These are exploratory outcomes to see if the compliance measures predict the benefits on the outcomes. This information is important for translation and information dissemination to people with MS.

To evaluate and compare the effectiveness between participants randomized to their preferred delivery mode (GEMS-T [Choice] or GEMS-S [Choice]) with those who are not randomized to their preferred delivery mode, we will use the same analysis model but examine an interaction term for choice and treatment. We will assess if the effect of Choice is the same for both treatments. Logistic regression will be used to assess the interaction between choice and adherence and attendance or dropouts. We also will examine time to dropout and/or time until dropout or poor compliance (which will be defined prior to final analyses). We also are interested in examining the intensity or compliance of the intervention to the choice as well as impact on the primary endpoint as noted above.

We will also utilize mediation analyses to understand if the changes induced by exercise are mediated via the changes in self-efficacy. Here we will use the approach by MacKinnon built on Judd and Kenny.⁴⁵⁻⁵¹ The MSWS-12, MFIS-21 and Neuro-QOL will all be analyzed using regression models similar to the timed walk models above and will utilize the same contrasts for examining choice as well as treatment effects.

DATA MANAGEMENT

The Data Management Center (DMC) will be housed at the Accelerated Cure Project/iConquerMS led by project co-investigator, [name]. The DMC will collaborate and communicate with the Steering Committee and Advisory Board as outlined in Table 4.

Table 4. Responsibilities/Tasks of Data Management Center (iConquerMS/[name])
Review the proposed trial protocol and contribute to finalizing that document
Develop electronic and paper case report forms for data collection
Develop Standard Operating Procedures and a study Manual of Procedures
Develop and maintain an electronic data management system that will include a web-based data entry system and project website for the study
Create, distribute and oversee data entry processes for all sites
Train and certify users from each site in the data entry
Receive, collect, process, store provide quality control and assist in data analysis of data collected from the participating clinical sites and central reading centers
Prepare and distribute periodic technical and statistical reports to the Steering Committee, participating sites, committees (including the DSMB) and the PCORI office, as appropriate

Data safety and adequacy

Each participant will be assigned a study ID number when they create an account after passing eligibility criteria. This will be the only identifier in all databases and systems used in this study. Each site investigator will have access to their own master file linking participants with their randomized assignment, but this file will be stored on the Portal and kept separately from participants' assessments.

Research data will be entered online through the secure portal system and source documents, such as the CRO forms, will be kept in a secure fashion. All hard copy documents, such as consent forms, will be kept in a locked cabinet, and all soft copy documents, such as screening and adherence logs, will be password protected.

To ensure the EDSS is performed uniformly across all sites, research coordinators will upload scanned, completed EDSS source documents to Shepherd Center's Microsoft 365 cloud. In order to ensure HIPAA compliance, Shepherd Center has a Business Associates Agreement (BAA) with Microsoft as well as appropriate security controls in place to ensure the confidentiality, integrity, and availability of the source documents.. Each research site will have their own site-specific folder to upload their EDSS forms to. EDSS forms should not contain any personally identifiable information, only the participant ID number and evaluator name.

For coaching audits, the coach will upload the file to their site-specific folder housed by UAB's Microsoft 365 cloud. UAB also have a BAA with Microsoft. Files will be labeled: [site name]_[wave #]_ session #_ date_participant ID. After uploading the file, the coach will delete the audio file from the recording device. Audio recordings will be stored on a password-protected computer on a server central to UAB. All audio data will be erased upon the completion of each wave of recruitment.

Copies of exercise log books will be uploaded to a site-specific Microsoft 365 cloud folder housed by UAB, saved with the participant's study ID.

Staff from iConquerMS will monitor and track errors, completeness with routine reports and feedback to the sites. Data will be shared with the Statistical Center at UAB, who will provide analyses using SAS, SPSS, R and other programs, as necessary.

Study portal security

The Portal components are created in the web content management system Drupal (<https://drupal.org/>). The Portal has design aspects that are sensitive to those with vision issues due to symptoms of the disease (e.g. color, size of type, etc.,) as well as compliance with Section 508 of the 1998 amended Rehabilitation Act. The portal has been designed to be usable on tablets and higher resolution smart phones to make it possible for all users – those with access to PCs or without – to participate. The portal's Survey Engine leverages the CURE framework, an enterprise data collection tool (eDCT) originally developed for the NIH-NCI (<https://github.com/NCIP/edct-formbuilder>).

Data collected through the Portal is stored in a commercial-grade, cloud-based, HIPAA compliant, secure data center. Data is backed up daily. Offsite backups may be held by a third party to guard against data loss.

Appropriate security measures have been put in place to minimize risks such as loss of confidentiality, identity theft, electronic fraud/security breaches, electronic monitoring, stalking or bullying, hacking, and phishing. Access to the data center is physically limited to authorized personnel. Password-protected access to the server will be granted to study staff and vendors with access permissions set based on their roles in the study. Data is encrypted at rest with keys available only to appropriate users. All data transmission (uploading and downloading) occurs over secure, encrypted channels.

Individual accounts requiring unique usernames and passwords will be created for participants. Identifiers will be stored separately from other data types to protect the privacy of individual participants. Data will be de-identified when viewed by anyone but the participants themselves and authorized study staff. ACP will legally require anyone accessing participant-contributed data to agree not to attempt to learn the identity of any participant, or present or publish data in which an individual can be identified.

STUDY SITE COORDINATION

This is a multi-site trial, with Shepherd Center as the prime site and eight other collaborating sites: the University of Alabama, Birmingham; the Tanner Center, Birmingham; the University of Georgia, Athens; the Cleveland Clinic Mellen Center for MS Treatment and Research, Ohio; the University of North Carolina, Chapel Hill; Massachusetts General Hospital, Boston; the University of Colorado; and Marquette University, Wisconsin.

Figure 4 presents the organizational structure for the study. [name] and [name] will provide oversight of all study activities.

[figure not shown]

Figure 4: Organizational Structure

Training

A Study Binder will be created that will specifically define all data collection and recording processes, and provided to each site. Training materials will be accessible electronically by all sites.

Shepherd Center investigators will train all collaborating sites in all study procedures as defined in this protocol, and provide each site with the Study Binder that will provide detail of all study procedures and processes. All research staff collecting outcomes will be trained in these procedures prior to the commencement of the study. This will include training in all recruitment and enrollment procedures for which they will use IRB-approved recruitment tools that we develop. We will provide each site with the appropriate forms for data collection, and training regarding recording procedures, as well as use of the study portal and database.

There will be an annual follow up at each site to ensure that processes and procedures are being followed with fidelity. If there is a change in the study personnel, the new personnel will be fully trained in the same processes and procedures. Data collection training will also be repeated annually. Data will be entered in the HIPAA-compliant, secure portal and maintained by iConquerMS with oversight by [name] and [name]. Sites will be responsible for maintaining all aspects of the database entered from the clinic, and staff support from iConquerMS will be available to trouble shoot technical questions. Access to this data will be restricted to study personnel only. Individual site coordinators will each have a unique username and password to enter the participant information.

The Project Manager will monitor enrollment numbers monthly to ensure that all sites are reaching milestones for recruitment. If one site is not reaching milestones, the co-PIs will reevaluate the recruitment strategy and determine if another site(s) can recruit/enroll more participants to cover the shortfall.

APPENDICES

Consent Script for Verbal Consent

Informed Consent Form

Informed Consent Form for Withdrawal - Early Termination Visit

Informed Consent Form for Withdrawal – Assessments Only

Recruitment Flyer

Social Media Recruitment Post

Staff CVs

CITI Certificates

Project Milestones

Fall prevention packet

